2.2. Study Objectives

2.2.1. Primary Objective

The primary objectives of the study are:

- To demonstrate target engagement, receptor binding/occupancy (RO) of pridopidine to sigma-1 receptors (S1R) in the brain (whole brain, cortical and subcortical regions) of healthy subjects and (optional) Huntington's disease (HD) patients after single oral dose administration;
- To establish the relationship between the plasma pridopidine concentrations and the S1R occupancy in the brain of healthy subjects and (optional) HD patients following a single oral dose of pridopidine.

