The PET imaging will consist of subsets of PET scans that will be acquired in list mode: 4 blocks with breaks in between. The first PET acquisition block of 90 minutes duration (0 to 90 minutes) will be started together with the intravenous injection of 300±30 MBq (S)-(-)-[¹⁸F]fluspidine; the following acquisition blocks of 30 minutes duration each will be started at 2, 3, and 6 hours post-injection of the PET tracer. Each PET acquisition block will be acquired in list mode in order to allow variable subdivision into multiple time frames as detailed in the imaging manual. In an effort to facilitate easier PET procedure for HD patients after the first 90-minute PET acquisition block, the subsequent 30-minute PET acquisition blocks are made optional per Investigator's judgement (refer to study Imagine Manual for details).

The first dose of pridopidine will be high (90 mg) for subjects enrolled in the first dose cohort but may be changed to another dose based on PRIDE-HD study results. Subsequent doses (0.5 or 1 mg in healthy subjects (Part A only); 2.5, 5, 10, 22.5, 45, or 67.5 mg in healthy subjects and HD patients; and a high dose of 112.5 mg in HD patients) will be determined on the basis of the RO results following PET session 2 and the time-activity profiles of (S)-(-)-[¹⁸F]fluspidine from previous cohort subjects. In addition, the timing of the PET sessions may also be revised. If any of the postdose PET investigations are compromised due to technical or logistic reasons, a repeat investigation may be considered, provided that the resulting cumulative radiation exposure by (S)-(-)-[¹⁸F]fluspidine for all PET sessions does not exceed the allowed overall study exposure (effective dose not exceeding 20 mSv), when using tracer administered activity of 300±30 MBq per PET session, and further respecting a washout of 7 days of pridopidine and its metabolites. PET session 2 will start at 2 hours postdose of pridopidine.

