3.3. Pharmacodynamic Measures and Time Points

- PET acquisition up to 390 minutes after injection of the tracer.

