3.5. Pharmacokinetic Measures and Time Points

Blood samples for analysis of pridopidine and the metabolite TV-45065 will be obtained prior to pridopidine dosing (<1 hour), at 5 (± 1 minute), 15, 30, 45 and 60 minutes after dosing (± 2 minutes), and at 1.5, 2, 2.5, 3, 4, 5, 6, 8, 12, and 24 hours after dosing. A 10-minute window will be allowed for all postdose sampling intervals from 1.5 hours up to and including 24 hours after dosing.

A description of the pharmacokinetic parameters is provided in Section [6.1](#).

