
^p The PET session 2 will take place at approximately a similar time of day (± 1 hour) as the baseline PET session 1, on another day (per PET slots scheduling availability). It will begin approximately 2 hours after pridopidine administration. The complete scan duration is 3 hours for both fluspidine and fallypride with breaks. Note: In an effort to facilitate easier PET procedure for HD patients, after the first 90-minute PET acquisition block, the subsequent 30-minute PET acquisition blocks are made optional per Investigator's judgement (refer to study Imaging Manual for details).

^q These should be done simultaneously to the dynamic list-mode PET scans.

^r Arterial blood samples for radioactivity levels will be obtained after administration of (S)-(-)-[^{18}F]fluspidine; a total of 51 samples (43×2 mL and 8×10 mL) will be collected at 39 time points during 210 minutes after injection of the tracer. Note: samples will not be collected for Part B.

^s Blood samples for analysis of pridopidine and the metabolite TV-45065 will be obtained prior to pridopidine dosing (<1 hour) at 5 (± 1 minute), 15, 30, 45 and 60 minutes after dosing (± 2 minutes), and at 1.5, 2, 2.5, 3, 4, 5, 6, 8, 12, and 24 hours after dosing. A 10-minute window will be allowed for all postdose sampling intervals from 1.5 hours up to and including 24 hours after dosing. Note: samples will not be collected for Part 0

^t At visit 3, blood will be collected for exploratory biomarker analysis on day -1 and on days 1 and 2 (prior to treatment, and at 4, 8, and 24 hours postdose; a 10-minute window will be allowed). For Part 0 where no treatment is given the time points corresponds to 2 hours prior to and 2, 6, and 22 hours post tracer injection.

^u Blood sampling for pharmacogenetics can be performed at a separate visit within the screening period after informed consent is obtained. Remnant sample will be retained for future exploratory analysis.

^v Adverse events inquiry and concomitant medication review will occur throughout the study. The period for adverse event reporting is defined as the time period from signing of the informed consent form through the end of the follow-up period. Conditions that worsen or events that occur after signing of informed consent will be recorded as an adverse event.

^w Medications administered following the first dose and throughout the study will be recorded as concomitant medication.

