5. TREATMENT OF SUBJECTS

5.1. Drugs Administered During the Study

5.1.1. Pridopidine

In this study, pridopidine can be administered as 0.5 or 1 mg in healthy subjects (Part A only); 2.5, 5, 10, 22.5, 45, 67.5, or 90 mg in healthy subjects and HD patients; and a higher dose of 112.5 mg may also be administered to HD patients. The applicable dose will be given selecting the lowest possible number of capsules. Pridopidine will be administered orally with 240 mL of water.

Study drug will be packaged in bottles and will be provided to the site for administration to subjects (see Section 3.9).

Lower dose study drugs will be packed in bottles on site (1 bottle per patient), prior to administration to the subjects.

5.1.2. [¹⁸F]fluspidine

The radiolabeled PET tracer [¹⁸F]fluspidine will be provided as a sterile, clear, colorless particle free solution to be administered intravenously for the neuroimaging of S1R brain receptors. The label on the tracer delivered for use in the PET scans will contain information regarding the composition of the product.

During the study period, the subjects will undergo a baseline PET investigation (PET session 1) and a post-treatment PET investigation during the study period (PET session 2) following a single oral dose of the study drug, pridopidine. On the day of each PET session, prior to PET imaging, a cubital or forearm vein will be cannulated to inject (S)-(-)-[¹⁸F]fluspidine (300±30 MBq) and, at visit 3, to obtain venous blood samples for quantification of pridopidine and its metabolite TV-45065 and other exploratory biomarker analysis. The subject's radial artery on the other arm (or the same arm if this cannot be achieved) will be cannulated to obtain arterial blood samples during PET imaging for the quantification of plasma radioactivity associated with (S)-(-)-[¹⁸F]fluspidine, in order to estimate a metabolite-corrected arterial plasma input function for PET data analysis. A total of 51 samples (43 × 2 mL and 8 × 10 mL) will be collected at 39 time points during 210 minutes after injection of the tracer. The arterial sampling intervals will be according to the institutional standards, as detailed in the study imaging manual.

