9.1. Sample Size and Power Considerations

This PET study is exploratory in nature; therefore, no formal hypothesis testing is planned. Thus, based on clinical and practical considerations, a sample size of up to approximately 38 subjects (up to 4 subjects per dose level) is considered adequate for this type of study and to attain the study objectives. Up to 45 subjects are planned to be enrolled in this study to ensure up to 38 evaluable subjects. Adaptive study design will allow increasing or reducing the study total sample size or each dose/time cohort as necessary. This sample size may include up to 4 patients with HD, which may be added to study engagement of pridopidine to the D2R and to explore the effects of neurodegeneration.

It is anticipated that 3 dose levels will be sufficient to characterize the exposure-response profile. However, additional cohorts may be studied.

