10. PHARMACODYNAMIC ANALYSIS

All pharmacodynamic analyses will be performed outside of the scope of this SAP and reported separately.

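### Does the optional late PET imaging for HD patients require a common scan window in the protocol or SAP?

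*Protocol*

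**What the plan says.** Protocol 3.1, 6.2.1.1 and 6.2.1.2 schedule four acquisition blocks for each tracer: 0-90, 120-150, 180-210 and 360-390 minutes after injection. Session 2 starts 2 hours after pridopidine (approximately, for fallypride). For HD patients, once the first block is done, "the subsequent 30-minute PET acquisition blocks are made optional per" the investigator's judgement. Footnotes o and p of Table 1 repeat this for sessions 1 and 2, and both footnotes and Section 3.1 point to the imaging manual for details.

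The length of imaging is described in two ways. Protocol 3.3 has "PET acquisition up to 390 minutes after injection of the tracer". Footnote p has "The complete scan duration is 3 hours for both fluspidine and fallypride with breaks". For fluspidine, arterial samples "will be collected at 39 time points during 210 minutes after injection of the tracer" (Protocol 5.1.2).

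The image analysis plan is placed in the imaging manuals (Protocol 2.3.1). The exposure-response analysis has its own plan (Protocol 9.7). SAP Section 10 states: "All pharmacodynamic analyses will be performed outside of the scope of this SAP and reported separately". SAP Section 11 does the same for the exposure-response work.

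On exposure, Protocol 9.7 defines C as the concentration that goes with the measured occupancy. Protocol 6.1 allows an average concentration over the scan where needed. Plasma sampling includes "1.5, 2, 2.5, 3, 4, 5, 6, 8, 12, and 24 hours after dosing" (Protocol 3.5).

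**The concern.** The HD cohort exists to see whether the healthy-subject findings carry over to patients (Protocol 1.7). A primary objective covers the "relationship between the plasma pridopidine concentrations and the S1R occupancy in the brain of healthy subjects and (optional) HD patients". If patients stop at 90 minutes and healthy subjects continue to 390, the two occupancy values describe different stretches of the drug's time course. With occupancy falling through the scan, the shorter window reads higher, so patients could appear more occupied for a reason unrelated to disease. If concentration were then averaged over the long window and paired with a 90-minute occupancy, EC50 in patients would come out too low. Nothing in the protocol or SAP names a common window, requires a patient's two sessions to use the same blocks, or sets a minimum number of blocks for evaluable imaging data.

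**Working it through.** **1. The plan's own figure.** Acquired time is 90 + 3 x 30 = 180 minutes, which is the 3 hours in footnote p. Elapsed time is 390 minutes, or 6.5 hours. The figure is therefore right without breaks, and the phrase about breaks is a slip. With session 2 starting 2 hours postdose, 0-90 minutes covers 2-3.5 h, 0-210 covers 2-5.5 h and 0-390 covers 2-8.5 h.

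**2. Simple time average.** The documents give no half-life, EC50 or tracer kinetics. Assume Emax 100%, mono-exponential decline from scan start with half-life h hours, and brain in step with plasma. With starting occupancy R0, let r(t) = [R0/(1-R0)] x 0.5^(t/60h) and RO(t) = r/(1+r), each acquired minute weighted equally.

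Example, R0 = 50% and h = 6: the block means are 47.8, 43.5, 40.7 and 32.7. The four-block mean is (90 x 47.8 + 30 x 43.5 + 30 x 40.7 + 30 x 32.7)/180 = 43.4, so the shift is 47.8 - 43.4 = 4.4 points. Stopping at 210 minutes, the mean is (90 x 47.8 + 30 x 43.5 + 30 x 40.7)/150 = 45.5, and the shift is 2.3.

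Shift in points, 0-90 minutes minus all four blocks:

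| Half-life | R0 30% | 50% | 70% | 90% | 99% |
|---|---|---|---|---|---|
| 4 h | 4.6 | 6.4 | 6.5 | 3.6 | 0.4 |
| 6 h | 3.3 | 4.4 | 4.2 | 2.1 | 0.3 |
| 8 h | 2.6 | 3.4 | 3.1 | 1.5 | 0.2 |
| 12 h | 1.8 | 2.3 | 2.0 | 0.9 | 0.1 |

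At 30-90% the range is 0.9-6.5. Against blocks to 210 minutes, where arterial sampling ends, it is 0.5-3.4. Near saturation it almost vanishes.

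**3. Allowing for 18F decay.** Equal weight per minute gives the late block too much influence. With weight 2^(-t/110) (110-minute half-life assumed), the 30-90% range falls to about 0.4-2.6. The protocol's own approximation, 24 hours for about 10 half-lives, implies 144 minutes and gives 0.4-3.2.

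**4. The sign.** Step 2 assumes that brain levels are already falling at 2 hours. With oral absorption (t_max 1-3 h), a brain delay with half-life 0-1 h, plasma half-life 4-12 h and equal weights, the shift runs from -2.6 to +6.5 points, with about a fifth of settings negative. At t_max 2 h, delay 1 h and half-life 8 h it is about -0.5.

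**5. The exposure-response curve.** If C is averaged over the window that produced the occupancy, the occupancy predicted from that average differs from mean occupancy by at most 1.5 points (half-life 4-15 h, starting occupancy 30-95%). The samples at 2, 2.5, 3 and 4 hours span 2-3.5 h. EC50 comes out 10-32% too low only if a 90-minute occupancy is paired with C over 2-8.5 h, which no section prescribes.

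**6. What a common 90-minute window would buy.** Take a simulated two-tissue model with 5% frame noise (assumed K1 0.35, V_ND 5, binding potential 4). With both sessions cut to 90 minutes, the SD of occupancy is 6.5, 13.4 and 30.3 points at k4 0.05, 0.02 and 0.01 per minute. With both sessions to 390 minutes it is 1.3, 1.4 and 1.5. For 4 against 4, SE = sqrt(SD1^2/4 + SD2^2/4):

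- all subjects on 0-90 minutes: 4.6, 9.5 and 21 points;
- patients on 0-90, healthy subjects on the full window: 3.3, 6.7 and 15 points.

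Within a patient, a full baseline paired with a 90-minute treatment scan gives median occupancy of 49.5-50.4 when the truth is a constant 50%. Unequal sessions therefore cost precision in this model and cause no material bias.

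**The case for a change.** The case for a change is reasonable. If occupancy is falling, the distortion has a fixed direction and more patients would not average it away. Replication in patients is the stated purpose of the cohort. The cure is cheap: every scanned subject is scheduled for a 0-90 minute list-mode block, so healthy data could be refitted with no change to scanning or blood sampling. The SAP was written against the protocol with Amendment 01 and describes four blocks without the HD option, so it gives no help.

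Part of this stands. The option is real, applies only to HD patients, and covers both tracers and both sessions. From these two documents alone a reader cannot tell which window an HD-healthy comparison would use, and a shift is possible. What does not stand is the step to a defect. The sections that grant the option send the reader to the imaging manual, and the image analysis plan and the exposure-response plan may well settle the matter. No stated rule gives a wrong answer. Neither the size nor the sign of the shift can be fixed from the documents, and the fallypride part has not been quantified at all.

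**Conclusion.** No change to the protocol or SAP follows. This is missing detail that belongs to, and may already sit in, plans outside these documents. An analyst who defines C as the concentration matching each occupancy value, with scan-window averages already foreseen, keeps most of the window effect out of the exposure-response curve.

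The possible shift is about -3 to +6.5 points across all assumed settings. It is at most about 3.4 points if the fit stops at 210 minutes under simple decline from scan start, and near zero at saturating occupancy. A forced common window would raise the standard error of a 4-against-4 comparison from 3.3-15 to 4.6-21 points in the assumed tracer model. That is as large as most of the shifts it is meant to remove, or larger. On numbers, Protocol 9.1 says "This sample size may include up to 4 patients with HD" and plans no formal testing; the cohort is optional, and the healthy-subject curve is unaffected by the option. Letting patients skip late blocks is a fair trade between tolerability and precision. A 90-minute refit of the healthy data remains available whenever someone wants it. The 3-hour wording in footnote p is clerical and changes no scheduled block.

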3.2. Justification for Study Design

The number of subjects studied per dose group is expected to be sufficient to meet the study objectives, which are not based on formal statistical hypothesis. Each dose-group will comprise up to 4 subjects (deviations will be allowed). An additional subject will be added if the results from 1 out of 3 subjects are discordant. It is anticipated that 3 dose levels will be sufficient to characterize the exposure-response profile (deviations will be allowed). However, additional cohorts may be studied. A cohort of HD patients may be added to study engagement of pridopidine to S1R and 2D receptors and to explore the effects of neurodegeneration in patients with HD.

3.3. Pharmacodynamic Measures and Time Points

- PET acquisition up to 390 minutes after injection of the tracer.

3.4. Safety Measures and Time Points

The following safety and tolerability measures will be implemented during the study:

- inquiries about adverse events at every visit
- clinical laboratory (serum chemistry, hematology, and urinalysis) tests on day -1 at visits 2 and 3 and at the follow-up (visit 4)
- vital signs (BP, respiratory rate, body temperature, and pulse) measured at every visit
- an ECG recorded at every visit
- physical examinations on day -1 at visits 2 and 3 and at the follow-up (visit 4)
- inquiries about use of concomitant medication at every visit

A description of the safety measures is provided in Section [7](#).

3.5. Pharmacokinetic Measures and Time Points

Blood samples for analysis of pridopidine and the metabolite TV-45065 will be obtained prior to pridopidine dosing (<1 hour), at 5 (± 1 minute), 15, 30, 45 and 60 minutes after dosing (± 2 minutes), and at 1.5, 2, 2.5, 3, 4, 5, 6, 8, 12, and 24 hours after dosing. A 10-minute window will be allowed for all postdose sampling intervals from 1.5 hours up to and including 24 hours after dosing.

A description of the pharmacokinetic parameters is provided in Section [6.1](#).

3.6. Exploratory Measures and Time Points

The exploratory/other efficacy measures and time points are:

- Endogenous corticoid plasma levels, taken directly prior to tracer dosing
- MR-AC, T1 MPRAGE 3D, ASL, MRS, and rs-fMRI scans in parallel with the PET imaging

- Blood exploratory biomarkers including prolactin, BDNF, monoamines and histamine metabolites up to 24 hours after dosing
- A pharmacogenetic blood sample will be collected at screening for genetic analyses of the CYP2D6 metabolizer status and S1R polymorphs

3.7. Randomization and Blinding

This is a non-randomized, open-label study and there is no blinding.

3.8. Maintenance of Randomization and Blinding

3.8.1. Maintenance of Randomization

Not applicable.

3.8.2. Blinding/Unblinding

This is an open-label study with no blinding.

3.8.3. Data Monitoring Committee

This study will not be overseen by a Data Monitoring Committee.

3.9. Drugs Used in the Study

3.9.1. Investigational Product - Pridopidine

Pridopidine will be provided as a white hard gelatin capsule, size 2 containing 45 mg pridopidine and a white hard gelatin capsule, size 4 containing 22.5 mg pridopidine or a light pink/white hard gelatin capsule, size 2, with black color imprinting containing 45 mg pridopidine and a white hard gelatin capsule, size 4, with black imprinting containing 22.5 mg pridopidine.

If lower pridopidine doses will be required, it will be prepared on site as follows:

- 0.5 and 1 mg - size 2 capsules will be filled with the appropriate amount of blend taken from the drug product capsules and diluted with [REDACTED]
[REDACTED]
- 2.5 mg pridopidine – size 2 capsules will be filled with the appropriate amount of blend taken from the drug product capsules
- 5 and 10 mg pridopidine – size 2 capsules will be filled with the appropriate amount of the active ingredient (neat)

A more detailed description of the preparation of lower doses can be found in the pharmacy manual.

A more detailed description of administration procedures is given in Section [5.1](#).

This is an uncontrolled study with no other study drug.

Additional details may be found also in the current IB for pridopidine.

3.9.2. PET Tracers

3.9.2.1. $[^{18}\text{F}]\text{fluspidine}$

The radiolabeled PET tracer $[^{18}\text{F}]\text{fluspidine}$ for the neuroimaging of S1R receptors with PET will be administered as a single intravenous bolus for each PET scan in Part A of the study, not exceeding 330 MBq and $<50\text{ }\mu\text{g}$ mass. (S)-(-)- $[^{18}\text{F}]\text{fluspidine}$ will be manufactured according to good manufacturing practice (GMP) daily, on an as-needed basis for use in the study, and provided as a clear, colorless, particle free solution consisting of 50 to 4000 MBq/mL (S)-(-)- $[^{18}\text{F}]\text{fluspidine}$, 7.5 mL sterile water for injection, 1.5 mL PEG400, 1 mL ethanol, and 0.1 mL of a concentrated sodium phosphate solution. The product will be packaged in TC-Elu-5 multidose containers [REDACTED] consisting of a colorless type 1 (Ph. Eur.) glass vessel which is sealed with a gray latex sulfur-free chlorbutyl rubber stopper covered with a blue aluminum and plastic flip-off seal.

The tracer will be labeled containing information regarding the composition of the product.

A more detailed description of administration procedures is given in Section [5.1](#).

3.9.2.2. $[^{18}\text{F}]\text{fallypride}$

The radiolabeled PET tracer $[^{18}\text{F}]\text{fallypride}$ will be administered as a single intravenous bolus for each PET scan in Part B of the study, not exceeding 220 MBq and $<2\text{ }\mu\text{g}$ mass.

(S)-(-)- $[^{18}\text{F}]\text{fallypride}$ will be manufactured according to GMP daily, on an as needed basis, for use in the study and provided as a clear, colorless, particle free solution consisting of 50 to 1000 MBq/mL $[^{18}\text{F}]\text{fallypride}$, 9 mL sterile isotonic saline solution for injection, 1 mL ethanol, and 0.1 mL of a concentrated sodium phosphate solution. The product will be packaged in TC-Elu-5 multi-dose containers [REDACTED] consisting of a colorless type 1 (Ph. Eur.) glass vessel which is sealed with a gray latex sulfur-free chlorbutyl rubber stopper covered with a blue aluminum and plastic flip-off seal.

The tracer will be labeled containing information regarding the composition of the product.

A more detailed description of administration procedures is given in Section [5.1](#).

3.10. Drug Supply and Accountability

3.10.1. Drug Storage and Security

The study drug (pridopidine) must be stored according to the manufacturer's drug product stipulation, in a dry place, and in a securely locked, substantially constructed cabinet or enclosure.

All study drug supplies must be stored at room temperature (15°C to 25°C/59°F to 77°F). Medication must not be refrigerated.

The tracers should be stored shielded, at room temperature (15°C to 25°C/59°F to 77°F).

Only authorized personnel will have access to the study drug. The study site personnel at the site will be responsible for correct storage and handling of the study drug.

